2.0 Background

2.1 Scientific Background and Gaps

According to the CDC, cigarette smoking is associated with profound morbidity and mortality. In the United States alone, cigarette smoking is responsible for about 443,000 deaths per year and it costs the nation nearly \$200 billion annually. About 20% of all adults smoke in the United States and by 12th grade, 42% of students report having smoked. Starting, however, is one problem and stopping is another. Cigarette smoking is a disease of chronic relapse. Indeed, once having started, smokers will make as many as 20 quit attempts before they are successful [1] and abstinence rates can be as low as 7%, even following NRT with the patch, gum, or nasal spray [2]. As with other addictions, cue-induced craving contributes to relapse following a quit attempt [3]. Along with cue-induced craving and relapse, addicts also suffer from drug-induced devaluation of natural rewards, as evidenced by less responding for a sweet in anticipation of the availability of drug in rats [4] and weaker responses to monetary rewards in striatum (a key brain reward region) in humans waiting to smoke [5, 6]. Importantly, those subjects (rats and humans) found least responsive to the natural reward are, in turn, most responsive to drug [4, 7].

From a global perspective, it would seem that there are three options for the treatment of cigarette smoking: no support (unaided cessation), behavioral support of one manner or another, and/or pharmacological intervention. With nearly 70% of smokers reporting that they would like to quit, yet most failing, we must assume that will, alone, is not sufficient. Certainly, the ability to quit any addiction can be bolstered by behavioral and/or pharmacological support. Contingency management is a behavioral intervention where abstinence is reinforced with tangible incentives such as money. However, and as alluded to, addicts may be insensitive to the very reward upon which their behavior is contingent. NRT is a long-standing and widely used smoking cessation tool. Yet, as discussed, NRT too is only modestly effective. We propose that the limited effectiveness of NRT is due, at least in part, to a failure to prevent cue-induced craving and relapse and to a failure to attenuate drug-induced devaluation of natural rewards. In support, NRT treatment does not attenuate either stimulus-elicited drug seeking [8] or the reduction in reward-related activity in the striatum of smokers [9]. Here we propose a novel alternative to the steady-state delivery of nicotine (i.e., to the standard patch) for the treatment of smoking cessation. Specifically, we propose to use an oral film to treat smokers wishing to quit with random, rather than steady-state, delivery of nicotine prior to and following the quit date.

2.3 Study Rationale

There is, as yet, no 'random patch'. Random delivery via a subcutaneously placed chip or pump is conceivable, but would be invasive and expensive. Here we propose to test the merits of our hypothesis, simply, by using an oral transmucosal dual-layer film that has been tested and is safe for use in humans [19, 20]. Plasma nicotine levels induced by the nicotine film are on par with those that accompany consumption of a similar dose of Nicorette gum. Preliminary pharmacokinetics studies found that 1mg films increased plasma nicotine levels by less than 2 ng/ml [21]. It has been demonstrated that smokers in a typical smoking day can reach plasma nicotine levels of up to 50 ng/ml [22]. The manufacturer of the film, [name], states that the 4mg film has been tested for taste in human nonsmokers and to the best of his knowledge was well-tolerated. [name], as a nonsmoker, has also taken an 8mg film without experiencing any ill effects. The film is easy to use and tastes pleasant to humans. No water is required, as the film simply adheres to the roof of the mouth until dissolved (about 5-10 min). Indeed, unlike nicotine gum, there are no complicated instructions regarding how and when to chew. The film can be used to deliver any dose of nicotine desired over time and placebo films are readily available. Finally, if the hypothesis proves correct, this novel treatment should be fairly inexpensive and available over the counter. As such, it will be both accessible and affordable, even for low-income smokers.

If this 'random film' were to work as predicted, cigarette cues would be dissociated from the act of smoking, sensitivity to alternative natural rewards would be enhanced and, most importantly, smokers maintained on the random film would be more likely to achieve cessation. This would be a remarkable advance for the treatment of smoking and would inform the treatment of other addictions as well.

3.0 Inclusion and Exclusion Criteria

3.1 Inclusion Criteria

1. Aged 18 - 55
2. Smoke >9 cigarettes/day for at least the past 12 months
3. Able to understand and consent to study procedures
4. Able to read and write in English
5. Exhaled Carbon Monoxide <12 ppm at in-person screening

3.2 Exclusion Criteria

1. Unstable or significant medical conditions and conditions such as elevated blood pressure (Systolic >140 mm Hg or Diastolic >90mm Hg at baseline), COPD and those that are likely to affect biomarker data such as kidney or liver disease.
2. Individuals with sodium-restricted diet, heart disease, recent heart attack, irregular heartbeat, stomach ulcers, or diabetes as well as those taking prescription medications for depression or asthma as indicated under "Warnings" section on FDA approved NRT Drug Facts Label.

3. More than weekly use in the past 3 months of illegal drugs or prescription drugs that are not being used for medically prescribed purposes or inpatient treatment for these in the past 6 months
4. Use of non-cigarette nicotine delivery product in the prior week (including cigars, pipes, chew, snus, hookah, electronic cigarette and marijuana mixed with tobacco)
5. Use of an FDA approved cessation medication in past week (any NRT, Chantix, Wellbutrin)
6. Women who are pregnant (verified by urine pregnancy test at visit), trying to become pregnant (not using a medically acceptable form of birth control for at least one month prior to visit i.e.: oral contraceptives, intrauterine device, double barrier), or nursing.
7. Uncontrolled serious psychiatric illness or inpatient treatment in the past 6 months
8. [23].
9. Unwillingness to provide blood samples or history of repeatedly fainting during blood draws
10. Any previous adverse reaction to NRT.
11. Any other condition, serious illness, or situation that would, in the investigator's opinion, make it unlikely that the participant could comply with the study protocol.

3.3 Early Withdrawal of Subjects

3.3.1 Criteria for removal from study

Participation may be discontinued if the principal investigator (PI) determines it is the best decision in order to protect the safety of a participant. The participant may be removed from the research study without his or her permission because the participant does not follow the instructions for the study, has an adverse reaction to the study product (irregular heartbeat, palpitations, tachycardia (resting heart rate persistently greater than 100 beats per minute), has symptoms of nicotine overdose such as nausea, vomiting, dizziness, weakness, or rapid heartbeat, or has symptoms of an allergic reaction.

3.3.2 Follow-up for withdrawn subjects

N/A

4.0 Recruitment Methods

4.1 Identification of subjects

All recruitment for this study will be routed through IRB STUDY00002213 which will also serve as the initial recruitment point of contact.

4.2 Recruitment process

Interested volunteers calling the study center number will first complete the eligibility script and questions for IRB STUDY00002213. If a participant's responses match our study's specified inclusion criteria they will be forwarded to the study coordinator for further screening.

4.3 Recruitment materials

See IRB STUDY00002213.

4.3.1 Eligibility/screening of subjects

Screening 1 (Phone): We will consider the screening process and eligibility questions in IRB STUDY002213 as Screening 1. Then, participants will complete the screening process in two additional steps.

Screening 2 (phone): A full script and screening questions for this study are in the "Consent Forms and Recruitment Materials" section of the IRB application.

Screening 3 (In person): After a participant has met basic eligibility criteria over the phone, they will be scheduled to come in to the study center where they will be

consented to the study and further screened for eligibility. See section 7.2 for further details.

5.0 Consent Process and Documentation

5.1 Consent Process

5.1.1 Obtaining Informed Consent

There will be separate consent forms for Part 1 and Part 2 of the study. Part 1 will accrue 12 participants after which it will be closed to enrollment and participants will only be able to enroll in Part 2, which will also accrue 12 participants. Part 2 will not be open to enrollment until Part 1 is complete. Participants will be informed of the part of the study that is currently open for enrollment.

5.1.1.1 Timing and Location of Consent

When participants attend their visit, they will have the appropriate part (1 or 2) of the study explained to them in detail, have the opportunity to ask questions and then will be asked to sign the appropriate consent form. Participants will be given a signed copy of the form. This will take place in a private clinic room at the Penn State Clinical Research Center (CRC).

5.1.1.2 Coercion or Undue Influence during Consent

Recruitment materials for the study will be broadly distributed throughout the community. Once participants contact the study center, they will be given information about the study and offered the opportunity to participate. The researchers obtaining consent will be instructed to clearly indicate that the participant's enrolling in the trial is purely voluntary and the researchers will not offer comments about whether they believe the participant should enroll in the study or not. Compensation provided to the participant for the study is modest.

5.1.2 Waiver or alteration of the informed consent requirement

N/A

5.2 Consent Documentation

5.2.1 Written Documentation of Consent

An IRB approved consent form will be used to document consent. Both the researcher and the participant will retain a copy of the consent. .

5.2.2 Waiver of Documentation of Consent

Participants who are interested in the study will be asked to consent to allow the researcher to pre-screen them for the study by asking all screening questions of all participants (eligible or ineligible). Participants will be asked if this information can be retained so that the study team will know reasons that participants are not eligible for the study.

In addition, participants who are not eligible for the study, or those who begin the phone screener but are not interested in completing it after learning more about the study, will be asked if they would be interested in being contacted for future studies being conducted by our research team. They will be informed that by providing their name and phone number, they will be consenting to allow the study team to contact them in the future.

5.3 Consent – Other Considerations

5.3.1 Non-English Speaking Subjects

N/A

5.3.2 Cognitively Impaired Adults

N/A

5.3.2.1 Capability of Providing Consent

N/A

5.3.2.2 Adults Unable To Consent

N/A

5.3.2.3 Assent

N/A

5.3.3 Subjects who are not yet adults (infants, children, teenagers)

5.3.3.1 Parental Permission

N/A

5.3.3.2 Assent

N/A

6.0 HIPAA Research Authorization and/or Waiver or Alteration of Authorization

6.1 Authorization and/or Waiver or Alteration of Authorization for the Uses and Disclosures of PHI

Check all that apply:

- Authorization will be obtained and documented as part of the consent process.
- Partial waiver is requested for recruitment purposes only
- Full waiver is requested for entire research study
- Alteration is requested to waive requirement for written documentation of authorization

6.2 Waiver or Alteration of Authorization for the Uses and **Disclosures** of PHI

6.2.1 Access, use or disclosure of PHI representing no more than a minimal risk to the privacy of the individual

6.2.1.1 Plan to protect PHI from improper use or disclosure

All data collected during the screening process will be directly entered into REDCap on a password protected, IT maintained, encrypted computer..

6.2.1.2 Plan to destroy identifiers or a justification for retaining identifiers

All study data will be retained indefinitely. Paper records will be kept in a safe area in [name] locked research office.

6.2.2 Explanation for why the research could not be practicably be conducted without access to and use of PHI

N/A

6.2.3 Explanation for why the research could not practicably be conducted without the waiver or alteration of authorization

In order to screen the participants prior to inviting them into the study center, the investigators are conducting a phone screen to determine if the participants are likely to be eligible for the study.

6.3 Waiver or alteration of authorization statements of agreement

Protected health information obtained as part of this research will not be reused or disclosed to any other person or entity, except as required by law, for authorized oversight of the research study, or for other permitted uses and disclosures according to federal regulations.

The research team will collect only information essential to the study and in accord with the 'Minimum Necessary' standard (information reasonably necessary to accomplish the objectives of the research) per federal regulations.

Access to the information will be limited, to the greatest extent possible, within the research team.

All disclosures or releases of identifiable information granted under this waiver will be accounted for and documented.

7.0 Study Design and Procedures

7.1 Study Design

This will be a randomized, double blind, parallel group pharmacokinetics study that will occur in two parts. The researchers and participants will be blind to the dosing of the nicotine films. Participants may participate in one or both parts of the study.

Part I: Participants are randomized to receive one dose of 0, 2, or 4 mg nicotine films

Part II: Participants are randomized to receive one dose every three hours for a total of four doses of either all 0 mg, all 2 mg or 4,4,0,4 mg nicotine films.

7.2 Study Procedures

Part 1- Screening (Phone)

Participants will be instructed to drink water prior to their visit to help the blood draw process go smoothly. They will also be instructed that they may choose to have a meal from our cafeteria but may also bring snacks if they would like. Participants will also be informed that they can bring personal items such as laptops, books, etc. for use during their visit.

Part 1-Screening (In Person)

Participants will be re-screened for eligibility and informed consent for the appropriate part of the study will be obtained by research staff.

After consent, additional eligibility screening materials will include:

1. A review of medications and medical history
2. NIDA Drug Screener
3. Blood Pressure (systolic must be \leq 140, diastolic must be \leq 90)
4. Urine pregnancy test (if applicable)
5. Exhaled Carbon Monoxide <12 ppm

Part 1 Visit – 4 Hours

Clinical measures and questionnaires will be conducted as outlined in the table below. An IV will be inserted for access for 11 blood draws in Part 1.

Part 1: Time and Events Table						
	Screening	Part 1 Procedures				
Visit Hour	-2	-1	0	1	2	3
Administer Film			X			
Blood Draws (mins)			0-59	60-119	120-179	180-239
Baseline Blood		X				
Hour 0 Blood			Set Minutes: 5, 10, 20, 30, 40, 50 Varied by Participant: 1 minute after film dissolves			
Hour 1 Blood				Minute 60		
Hour 2 Blood					Minute 120	
Hour 3 Blood						Minute 180
Measures						
Screener 2	X					
Concomitant Meds	X					
Medical History	X					
NIDA	X					
CES-D		X				
Oropharyngeal Exam		X				X
Blood Pressure & Heart Rate	X	X	Minute 30	Minute 0, 30	Minute 0, 30	Minute 0, 30
CO Reading	X					X
Pregnancy Test	X					
Anthropometrics		X				
Demographics		X				
Nicotine Dependence		X				
Cigarette Details		X				
Tobacco Use History		X				
Minnesota Withdrawal Scale		X	Minute 15, 35, 55	Minute 20	Minute 20	Minute 20
Questionnaire of Smoking Urges		X	Minute 15, 35, 55	Minute 20	Minute 20	Minute 20
Study Product Side Effects			Minute 15, 35, 55	Minute 20	Minute 20	Minute 20
Study Product Evaluation						X
Likelihood of Use Scale						X
Payment						\$120

Film Administration, Dose and Blood Draws:

Participants will receive one film at this visit after completing baseline measures (approximately 8 AM). They will be instructed to allow the film to dissolve in their mouth without chewing or swallowing it and to report to the researcher when he or she feels that the film has completely dissolved. Four participants each will receive a randomly allocated dose of either (a) 0mg, (b) 2mg or (c) 4mg oral nicotine film. The Time and Events table above details the order of events and timing for biomeasures, questionnaires and 11 total blood draws. However, if the film dissolves within one minute of a set blood draw time, the blood draw that is to be completed one minute after the film dissolves will be omitted.

Payment:

Participants will receive \$120 for completing this visit.

Part 2- Screening (Phone)

Participants will be instructed to drink water prior to their visit to help the blood draw process go smoothly. They will also be instructed that they may choose to have meals from our cafeteria but may also bring snacks if they would like. Participants will also be informed that they can bring personal items such as laptops, books, etc. for use during their visit.

Part 2- Screening (In Person)

Participants will be re-screened for eligibility and informed consent for the appropriate part of the study will be obtained by research staff.

After consent, additional eligibility screening materials will include:

1. A review of medications and medical history
2. NIDA Drug Screener
3. Blood Pressure (systolic must be \leq 140 mm Hg, diastolic must be \leq 90 mm Hg)
4. Urine pregnancy test (if applicable)
5. Exhaled Carbon Monoxide <12 ppm

Part 2 Visit- 12 hours

Clinical measures and questionnaires will be conducted as outlined in the table below.

An IV will be inserted for access for 20 blood draws in Part 2. Time and contents of participant meals/snacks will also be recorded so as to enable researchers to assess food intake and timing as it relates to timing of nicotine absorption from the film.

Part 2: Time and Events Table														
	Screening		Part 2 Procedures											
Study Hour	-2	-1	0	1	2	3	4	5	6	7	8	9	10	11
Administer Film			X			X			X			X		
Blood Draws														
Baseline Blood		X												
Hour 0 Blood			Min 30, 45											
Hour 1 Blood				Min 0										
Hour 2 Blood					Min 0									
Hour 3 Blood						Set Mins: 0, 30, 45								
Hour 4 Blood							Min 0							
Hour 5 Blood								Min 0						
Hour 6 Blood									Set Mins: 0,30,45					
Hour 7 Blood										Min 0				
Hour 8 Blood											Min 0			
Hour 9 Blood												Set Mins: 0, 30,45		
Hour 10 Blood													Min 0	
Hour 11 Blood														Min 0
Study Hour	-2	-1	0	1	2	3	4	5	6	7	8	9	10	11
Measures														
Screener 2	X													
Concomitant Medications	X													
Medical History	X													
NIDA	X													
CES-D	X													
Oropharyngeal Exam		X												X
Blood Pressure & Heart Rate	X	X	Min 30	Min 0, 30	Min 0, 30	Min 0, 30	Min 0, 30	Min 0, 30	Min 0, 30	Min 0, 30	Min 0, 30	Min 0, 30	Min 0, 30	Min 0
CO Reading	X													
Pregnancy Test	X													
Anthropometrics	X													
Demographics	X													
Dependence	X													
Cigarette Details	X													
Tobacco Use History		X												
Minnesota Withdrawal Scale		X	Min 50	Min 50		Min 50	Min 50		Min 50	Min 50		Min 50		Min 50

Questionnaire of Smoking Urges		X	Min 50	Min 50		Min 50	Min 50		Min 50	Min 50		Min 50	Min 50
Study Product Side Effects			Min 50	Min 50		Min 50	Min 50		Min 50	Min 50		Min 50	Min 50
Study Product Evaluation						Min 0							X
Likelihood of Use Scale						Min 0							X
Dose Awareness													X
Payment													\$240

Film Administration, Dosing and Blood draws:

Participants will receive four doses of nicotine film during this visit. Four participants each will be randomly allocated to consume four films over twelve hours in the following orders (a) 0,0,0,0mg (b) 2,2,2,2, or (c) 4,4,0,4. The first film will be administered upon completion of baseline measures (approximately 8AM). Again, participants will be instructed to allow the film to dissolve in their mouth, without chewing or swallowing it and to report to the researcher when he or she feels that the film has completely dissolved. Films will be administered every three hours (approximately 11 AM, 2 PM, and 5 PM). The Time and Events table above details the order of events and timing for biomeasures, questionnaires and 20 total blood draws.

Payment:

Participants will receive \$240 for completing this visit.

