7.4 Test Article(s) (Study Drug(s) and/or Study Device(s))

7.4.1 Description

Nicotine orally dissolving films (ODF) will be provided in doses of 0, 2, or 4 mg. The active pharmaceutical ingredient in Nicotine ODF is nicotine polacrilex (20%, USP). The film used in Nicotine ODF has a muco-adhesive property, i.e. it can adhere to the oral mucosa and allow the drug to be absorbed through oral mucosa. After placement in the oral cavity, nicotine ODF dissolves over a 5-10 minute period. The unit-dose dosage is in the form of a 1 in x 1 in square and weighs about 100 mg. Nicotine films are not available in the United States in a non-investigational setting. See table below for composition information.

Nicotine Oral Film Formulations: 0, 2, and 4 mg

Nicotine ODF Dosage		Placebo, 0 mg	2 mg	4 mg
Material Name	Grade	Weight, g		
Sodium Bicarbonate	USP/EP	1.97	1.71	1.64
Propylene Glycol	USP/EP	23.66	20.55	19.68
Nicotine Polacrilex 20%	USP	0.00	17.81	37.72
Purified Water	USP	209.04	205.45	196.80
Ethanol anhydrous	USP	110.44	119.85	114.80

Polyox N10 (Polyethylene oxide)	NF	134.10	116.42	111.52
Saccharin	Food Grade	2.45	2.12	2.03
Cocoa Powder	Food Grade	1.77	1.71	1.97
L-Menthol	USP	9.98	8.66	8.30
Peppermint oil	USP	6.19	5.38	5.15
Methylparaben	NF	0.20	0.17	0.20
Propylparaben	NF	0.20	0.17	0.20
Total		500.00	500.00	500.00

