11.5 Individual's reviewing the data

The study coordinator will be responsible for the daily oversight of subject safety and will provide updates to the Principal Investigators to review participants' progress and their experiences with the study, including any adverse events.

In the event of adverse event(s) during the conduct of the study, we have a mechanism in place to ensure that the event(s) will be assessed by the Principal Investigators and the study physician and reported to the PSU IRB and NIH in a timely manner. All adverse events (AEs) occurring during the course of the study must be collected, documented, and reported to the Principal Investigators and [name], Professor of Medicine and Chief of Division of Internal Medicine at Penn State Hershey,. All AEs will be assessed by the Principal Investigator to determine if they meet criteria for a serious adverse event (SAE). Serious adverse events, as defined by the FDA, will be systematically evaluated at each clinic visit. Any SAE, whether or not related to study participation, will be reported to the IRB, and NIDA. The initial SAE report will be followed by submission of a completed SAE report. Outcome of SAEs will be periodically reported to NIDA. A summary of the SAEs that occurred during the previous year will be included in the annual progress report to NIDA. Each week a study investigator will review the AE Forms from the previous week for events that were reported as new or continuing. The study investigators will follow all AEs to the point of a satisfactory resolution. A study participant may have their participation discontinued if the PI determines it is the best decision in order to protect the safety of a participant.

Where any participant had a serious adverse event (systolic BP>160, vomiting or any other symptoms requiring their participation in the study to be interrupted/terminated), [name] will immediately review the case and make a recommendation both on management of that individual case but also continuation of the study at the planned doses.

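### No heart rate or blood pressure reading is scheduled in the first 30 minutes after any film, so a short early rise may go unrecorded

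*Combined protocol and SAP*

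**What the plan says.** **Timing of the readings.** The row "Blood Pressure & Heart Rate" appears in both tables of section 7.2.

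- Part 1: a reading at screening (hour -2) and at hour -1, then minute 30 of hour 0, then minutes 0 and 30 of hours 1 to 3.
- Part 2: the same two pre-film readings, then minute 30 of hour 0, minutes 0 and 30 of hours 1 to 10, and minute 0 of hour 11. Films are given at hours 0, 3, 6 and 9: "Films will be administered every three hours (approximately 11 AM, 2 PM, and 5 PM".

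**Timing of the exposure.** Section 7.4.1: "After placement in the oral cavity, nicotine ODF dissolves over a 5-10 minute period". Sections 2.3 and 7.4.2 give the same range. The Part 1 hour 0 blood row reads "Set Minutes: 5, 10, 20, 30, 40, 50 Varied by Participant: 1 minute after film dissolves". The Part 1 row "Study Product Side Effects" starts at minute 15.

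**Use of the readings.** Sections 9.2 and 11.7 name HR and BP among the outcome measures tested for change from baseline, and 11.2 lists them as reviewed safety data. Section 3.3.1 allows removal for, among other things, "tachycardia (resting heart rate persistently greater than 100 beats per minute". Section 11.5 calls for immediate case review for "systolic BP>160, vomiting or any other symptoms requiring their participation in the study to be interrupted/terminated". Under 11.6, all Part 1 data are reviewed before Part 2 starts, and doses or blood-sampling times may then be adjusted.

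**The concern.** The plan treats the first 20 minutes as worth sampling for plasma nicotine in Part 1, but takes no cardiovascular reading there. A rise in HR or BP that began and ended before minute 30 would leave no trace in the scheduled data. Three uses are exposed:

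- **Outcome.** The change from baseline would be described only from minute 30 on, and up to four early plasma levels in Part 1 would have no matching HR or BP value.
- **Part 1 review.** The group deciding whether Part 2 goes ahead as planned would see early plasma levels and early side effects, but no early HR or BP.
- **Systolic trigger.** This rule acts on a measured value. Section 7.2 admits participants with systolic pressure up to 140, so someone at that limit needs a rise of just over 160 - 140 = 20 mm Hg to cross it. A brief rise of that size without symptoms could pass unseen.

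**Working it through.** **1. Check that the tables were read correctly.** The plan states 11 draws in Part 1 and 20 in Part 2.

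- Part 1: 1 baseline + 6 set draws in hour 0 + 1 after dissolution + 3 (minutes 60, 120, 180) = 11.
- Part 2: 1 baseline + 2 (hour 0) + 2 (hours 1, 2) + 3 × 3 (hours 3, 6, 9) + 6 (hours 4, 5, 7, 8, 10, 11) = 20.

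Both totals are reproduced.

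**2. First HR/BP reading strictly after each film.**

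| Film | Readings in the next hour (min after film) | Readings between 0 and 30 min |
|---|---|---|
| Part 1, single film | 30, 60 | none |
| Part 2, hour 0 | 30, 60 | none |
| Part 2, hours 3, 6 and 9 | 30, 60 | none |

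The minute 0 readings at hours 3, 6 and 9 fall at the time of the film itself, so they cannot show that film's effect.

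**3. Delay after dissolution.** Delay = reading time - dissolution time.

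- Now: 30 - 10 = 20 to 30 - 5 = 25 min.
- With a reading at minute 10: 0 to 5 min. At minute 15: 5 to 10 min. At minute 20: 10 to 15 min.

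**4. Films affected.**

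- Part 1: 12 films, 4 + 4 = 8 with nicotine.
- Part 2: 12 × 4 = 48 films. With nicotine: 4 × 4 = 16 of 2 mg, plus 4 × 3 = 12 of 4 mg (the third film in that arm is 0 mg), so 28.
- Total: 60 films, 8 + 28 = 36 with nicotine, none with a reading before minute 30.

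**5. What else is scheduled strictly between 0 and 30 minutes.**

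- Part 1: draws at 5, 10 and 20 min, one more a minute after dissolution (about 6 to 11 min, omitted if it falls within a minute of a set draw), and questionnaires at minute 15. Of the 10 post-film draws, 4 (30, 60, 120, 180) share a minute with an HR/BP reading.
- Part 2: nothing. The first draw is at minute 30 and the first side-effect questionnaire at minute 50.

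**6. What cannot be calculated.** The share of any peak still visible at minute 30 depends on the time to peak and the rate of decline. The documents give neither for plasma nicotine, HR or BP. Section 2.3 likens the levels to those from gum but states no time.

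**The case against.** The strongest reply is that dissolution is not peak effect. The plan does not single out the first 20 minutes: Part 1 also draws at 30, 40, 50 and 60 minutes, and Part 2 first draws at 30. An effect that peaks near minute 30, or lasts until then, is captured. This stands, and it limits the point to what may be missed.

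A reader might also infer that the safety rules cannot work in the first half hour. The documents do not support that. The heart-rate criterion asks for persistence, which readings at 30 and 60 minutes can show. Sections 3.3.1 and 11.5 also act on symptoms such as dizziness, nausea and vomiting, with no confirming reading required. Participants are supervised throughout (12.0), with trained nurses and a physician or designee on site (11.1), and nothing bars an unscheduled reading. Only the systolic trigger is exposed, and only for a brief rise without symptoms.

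Nor is a pre-film baseline missing: both tables have a reading at hour -1, and the film follows the baseline measures.

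The stakes are modest too. The primary endpoint is plasma nicotine, the secondary is subjective ratings and side effects, and there are four participants per arm. The first 20 minutes of Part 1 are already busy, with up to four draws and three questionnaires.

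What remains is that supervision and unscheduled readings do not give comparable data at fixed times. The absence of a stated time to peak also means that the plan gives no ground for relying on minute 30 to catch the maximum.

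**Conclusion.** The point holds in a limited form and is worth acting on. Neither part schedules an HR or BP reading in the first 30 minutes after any film, and the first one comes 20 to 25 minutes after dissolution. A short early rise may therefore go unrecorded, both as a named outcome and against the systolic trigger. The gap is wider in Part 2, where dosing is repeated and no scheduled measurement of any kind falls strictly within the half hour after a film.

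Two stronger conclusions are not supported: that an early effect is in fact missed, and that the peak is understated by some stated fraction. Either would need a time to peak that the documents do not give. The primary endpoint is not affected.

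The conclusion rests on the tables as printed, on the stated dissolution range of 5 to 10 minutes, and on no unscheduled readings being taken.

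**What to change.** **Part 1.** Add HR/BP readings at the existing 10- and 20-minute draws, with the cuff on the arm without the IV. Draws with a same-minute reading rise from 4 to 6 of 10.

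**Part 2.** Add one HR/BP reading at about minute 15 after each of the four films.

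**Analysis.** Report the change from the existing pre-film reading at each time point, and the largest change within 60 minutes of each film. For films 2 to 4, state that the minute 0 reading is taken before the film is placed, since the table gives no order. Show both summaries by arm and alongside the 0 mg arm. The largest of several readings is biased upward even without a drug effect, and the number it is taken over would rise from 2 to 4 per film in Part 1 and from 2 to 3 in Part 2. The largest change should therefore not be tested against zero within an arm, or compared between parts, as if it were a single reading.

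**Cost.** Two more cuff readings per Part 1 participant (7 to 9 after the film) and four per Part 2 participant (22 to 26 after the first film). That is 12 × 2 + 12 × 4 = 72 in all, taken by staff already present. The downside is a busier first half hour, mainly in Part 1. No dose, threshold or removal rule changes.

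### Does the untimed baseline blood draw before the first film undermine the change-from-baseline analysis of plasma nicotine?

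*Combined protocol and SAP*

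**What the plan says.** Section 7.2 points to the tables for sampling times: "The Time and Events table above details the order of events and timing for biomeasures, questionnaires and 11 total blood draws" in Part 1 and "The Time and Events table above details the order of events and timing for biomeasures, questionnaires and 20 total blood draws" in Part 2. In each table the row "Baseline Blood" holds a bare X under Hour -1. The post-film draws have set minutes, apart from one Part 1 draw timed from when the film dissolves. In Part 2, the hours of films 2 to 4 each include a minute-0 draw (for Hour 3, "Set Mins: 0, 30, 45"), so those films have a sample at dosing. The first film has none.

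Film timing is given relative to the baseline block: "Participants will receive one film at this visit after completing baseline measures (approximately 8 AM" in Part 1, and in Part 2 "The first film will be administered upon completion of baseline measures (approximately 8AM".

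Sections 9.2 and 11.7 plan a paired test of change from baseline. Section 3.1 requires "Exhaled Carbon Monoxide <12 ppm at in-person screening". No section states a cigarette abstinence period. Section 4.3.1 says "A full script and screening questions for this study are in the" recruitment materials filed with the IRB application, which are not part of these documents.

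**The concern.** Plasma nicotine is the primary endpoint (section 1.2), and the only planned test compares later values with this one sample. Participants smoke more than nine cigarettes a day and may arrive with nicotine still in the blood. The carbon monoxide limit restricts recent heavy smoking but does not measure nicotine.

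If blood is drawn early in the baseline block, residual nicotine keeps falling until the film is given. That fall enters every change score with a negative sign. If the gap differs between participants, it also adds noise in groups of four. The expected signal may be small: section 2.3 reports a rise of less than 2 ng/mL for a 1 mg film. An unset gap could therefore take up a noticeable part of the measured rise.

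**Working it through.** **Is there an unlisted pre-film draw?** Counting the table entries:

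- Part 1: 1 baseline + 6 set times in Hour 0 + 1 after dissolution + 3 hourly = 11.
- Part 2: 1 + 2 + 1 + 1 + 3 + 1 + 1 + 3 + 1 + 1 + 3 + 1 + 1 = 20.

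Both match the stated totals, so there is no minute-0 draw before the first film. The first later samples come at minute 5 (Part 1) and minute 30 (Part 2).

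**How long could the gap be?** Besides the blood, the Hour -1 column lists ten items in Part 1 and five in Part 2 (an oral examination, blood pressure with heart rate, and three questionnaires). No order is given among them. If the draw comes last, the gap is close to zero. If it comes first, the one-hour column suggests up to about 60 min, though no section states that limit.

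**How large could the fall be?** Pre-film fall = residual × (1 − 2^(−gap/half-life)). The documents give neither a residual level nor a half-life, so both are assumed. Results in ng/mL for half-lives of 1 / 2 / 3 h:

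| Gap | Residual 2 ng/mL | Residual 5 ng/mL |
|---|---|---|
| 5 min | 0.11 / 0.06 / 0.04 | 0.28 / 0.14 / 0.10 |
| 30 min | 0.59 / 0.32 / 0.22 | 1.46 / 0.80 / 0.55 |
| 60 min | 1.00 / 0.59 / 0.41 | 2.50 / 1.46 / 1.03 |

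**Against what signal?** Scaling the section 2.3 bound in proportion to dose (a further assumption) gives less than 2 × 2 = 4 ng/mL for 2 mg and less than 4 × 2 = 8 ng/mL for 4 mg. The 60 min fall as a share of those ceilings is:

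- Residual 2 ng/mL: 10–25% (0.41/4 to 1.00/4) for 2 mg and 5–13% for 4 mg.
- Residual 5 ng/mL: 26–63% (1.03/4 to 2.50/4) for 2 mg and 13–31% for 4 mg.

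At a 5 min gap and 5 ng/mL, the shares are 2–7% and 1–4%. If the true rises lie below the ceilings, all these shares are larger; if above, smaller.

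**What would a timed draw remove?** Only decay before the film. The share of total decay, from draw to sample, that is pre-film equals (1 − 2^(−gap/h)) / (1 − 2^(−(gap + t)/h)), where h is the half-life and t the sample time after the film. It does not depend on the residual level. For half-lives of 1 / 2 / 3 h:

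| Gap | Sample at minute 30 | Sample at minute 180 |
|---|---|---|
| 60 min | 77 / 72 / 70% | 53 / 39 / 34% |
| 5 min | 17 / 16 / 15% | 6 / 4 / 4% |

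At short gaps nearly all the decay comes after the film, where the time of the baseline draw has no influence.

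**The case for a change.** The best case for a change is that this sample is the reference for the primary analysis, that the protocol sets minutes for almost every other draw, and that fixing this one would cost almost nothing and add no blood. The 0 mg arm is sampled on the same schedule, so a contrast with it would remove the fall in expectation, but section 9.2 plans no such contrast and four per arm may not balance the gaps. Part 1 nicotine results also inform the decision to start Part 2 (section 11.6).

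The factual core stands: neither the order nor the gap is written down. The inference of harm is weaker.

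- The film is tied to the end of the block, and taking the blood last is fully compliant.
- The larger percentages need the higher residual, the full inferred hour and dose proportionality all at once.
- In Part 1, a baseline drawn too early would tend to show itself, because sampling starts at minute 5 and the 0 mg arm shows decay directly. Part 2, with its first sample at minute 30, lacks this early check.
- Section 11.6 allows sampling times to be adjusted before Part 2. That cannot repair Part 1, but it gives a documented route if Part 1 reveals a problem.
- The concentrations measured after the film, which the review between parts will also see, do not depend on when the baseline was drawn.

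The missing contrast with 0 mg is the more basic limitation. Post-film decay would remain even with a perfectly timed baseline.

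**Conclusion.** No change to the plan is needed. The tables leave out a minute and an order for one draw. Site staff can settle this in the ordinary course of running the visit, and no stated rule is shown to produce a wrong result.

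The possible effect runs from nil, if blood is drawn last, to 0.4–2.5 ng/mL at an inferred 60 min gap. That range rests on assumed residuals of 2 to 5 ng/mL and half-lives of 1 to 3 h. The documents cannot narrow it, and they do not show that gaps will be long or uneven. The bias would understate the rise, which is the cautious direction for a claim that the film delivers nicotine.

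The judgement would be different if the visit procedures placed the blood draw routinely at the start of the baseline block in participants who had recently smoked. Nothing in the protocol says so.
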